## **C2: Three-dose Scheme**

Intervention group: Intramuscular injection (Deltoid muscle) of 25 µg SOBERANA-02 vaccine on days 0 and 28 as well as a third dose with SOBERANA-plus on day 56

Placebo group: Intramuscular injection of placebo on days 0, 28 and 56

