## **4. Study Procedures and Assessments**

### **4.1 Efficacy Assessment**

The vaccine efficacy will be considered in terms of the prevention of symptomatic COVID-19 infection (as the primary outcome), as well as severe COVID-19 infection and COVID-19-related

death (as secondary outcomes), all of which will be considered in efficacy analysis if they occurred from 14 days after the second/third dose onward.

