## **6.2 The Statistical Analysis Plan**

### ***6.2.1 Efficacy population***

To analyze the efficacy, we will apply by “Intention to treat (ITT)” analysis.

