### **6.3 Statistical tests**

We will apply the stratified Cox regression model to estimate vaccine efficacy. The efficacy will be reported using the “1-Hazard Ratio”. Also, vaccine efficacy will be estimated through a logistic regression on the long person-time format dataset using a working correlation matrix. In this model, the efficacy will be reported using the “1-OR”.

In each study arm (placebo vs. treatment), the frequency of adverse reactions or events will be described and estimated with 95% CI. The seroconversion frequency (cases with a four-fold rise in S antibody titer compared to the base) will also be described with 95% CI in each study arm. Furthermore, the geometric mean of the antibody titer will be calculated and reported with a 95% CI. Antibody titers between the vaccine and placebo groups will be compared with Mann-Whitney U. Also mean difference and the mean ratio will be calculated. The frequency of serious and unsolicited adverse events will be separately described and categorized system-by-system. The affected body systems are based on the classification in the “Medical Dictionary for Regulatory Activities” (MedDRA). All statistical analyses will be performed with R and Stata software (v. 16).

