**Outcomes**

**Primary Outcome**

Outcome	Definition	Measurement method	Timing of measurement
Symptomatic COVID-19-19 infection	Identification of SARS-CoV-2 RNA (two viral gene targets) in the respiratory samples of suspected cases	Real-time PCR	
C1: From day 14th after the 2nd dose until the end of efficacy study time
 
C2: From day 14th after the 3rd dose until the end of efficacy study time

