All volunteers will be instructed to coordinate with the call center and go to designated laboratories for a PCR test quickly within 48 hours in case of presenting with two or more of the following symptoms lasting for over 24 hours confirmed in positive PCR testing: Fever (temperature  $\geq 38^{\circ}\text{C}$ ), chills, new cough, sore throat, nasal congestion, fatigue, muscle or body pain, headache, nausea or vomiting, diarrhea, loss of smell or taste, or at least one respiratory sign or symptom (i.e., cough, O2 saturation  $< 91$ , shortness of breath, or clinical or radiographic evidence of pneumonia).

3) Nasopharyngeal and pharyngeal swabs will be taken from the symptomatic volunteer. If the volunteer cannot be present in the lab, the operator arranges a home visit/s for him/her to take samples and clinical assessment/s. If the home visit is impossible, the symptomatic volunteer is asked to make a pharyngeal gargle with a standard method and then bring it to the lab. If PCR turns to be negative yet the symptoms last for more than 2 days, the test will be repeated after 7 days. The volunteers with positive tests who do not need hospitalization will be visited by Phone daily until full recovery of symptoms. It is important

to take note that some manifestations of COVID-19 have overlapped with systemic AEs following immunization (e.g., myalgia, headache, fever and chills). Regarding that such AEs are more common within 3 days following vaccination in case of having other symptoms of COVID-19, an infectious disease specialist judges clinically and decides whether a sample for PCR is needed. All PCR-positive cases after the 2nd shot will be counted and included to estimate vaccine efficacy (primary outcome).

4) The volunteer must record all solicited local and systemic AEs within the first 72 hours post-vaccination in their online profiles. If any volunteer did not complete the diary, an active follow-up will be done on day four. Moreover, unsolicited adverse events will be followed up 28 days after each dose, and medically attended adverse events and serious adverse events will be monitored six months after the first dose.

5) All medical treatments and other vaccines received within the 28 days after each vaccine dose as well as AEs and SAEs will be recorded. All SAEs which need medical intervention will be recorded from screening day (Day 0) till the end of follow-up (6 months after the first dose).

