- 3) All volunteers will be instructed to coordinate with the call center and go to designated laboratories for PCR tests quickly within 48 h. Nasopharyngeal and pharyngeal swabs will be taken from the symptomatic volunteer. If the volunteer cannot be present in the lab, the operator arranges a home visit/s for him/her to take samples and clinical assessment/s. If a home visit is impossible, the symptomatic volunteer is asked to make a pharyngeal gurgle with a standard method and then bring it to the lab. If PCR turns to be negative yet the symptoms last for more than 2 days, the test will be repeated after 7 days. The volunteers with positive tests who do not need hospitalization will be visited by Phone daily until full

recovery of symptoms. It is important to take note that some manifestations of COVID-19 have overlapped with systemic AEs following immunization (e.g., myalgia, headache, fever and chills). Regarding that such AEs are more common within 3 days following vaccination in case of having other symptoms of COVID-19, an infectious disease specialist judges clinically and decides whether a sample for PCR is needed. All PCR-positive cases after the 2nd shot will be counted and included for the estimation of vaccine efficacy (primary outcome).

4) Blood samples will be taken from 2,000 volunteers in Zanjan city for serologic assay on days 0 and 84.

5) The volunteer must record all solicited local and systemic AEs within the first 72 hours post-vaccination in their online profiles. If any volunteer did not complete the diary, an active follow-up will be done on day four. Moreover, unsolicited adverse events will be followed up 28 days after each dose, and medically attended adverse events and serious adverse events will be monitored for seven months after the first dose.

6) All medical treatments and other vaccines received within the 28 days after each vaccine dose as well as AEs and SAEs will be recorded. All SAEs which need medical intervention will be recorded from screening day (Day 0) till the end of follow-up (7 months after the first dose).

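### Note 3 of Tables 1 and 2 starts primary-outcome counting at the second dose, against section 4.1 and the outcome table; in the three-dose cohort that is 42 days early

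*Protocol*

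**What the plan says.** Section 4.1 names the efficacy outcomes, "all of which will be considered in efficacy analysis if they occurred from 14 days after the second/third dose onward". The Primary Outcome table gives the same start by cohort. For C1 the window opens on day 14 after the second dose, and for C2 it is "From day 14 th after the 3 rd dose until the end of efficacy study time".

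Note 3 to the activity tables describes how symptomatic volunteers are swabbed and followed up. Its last sentence sets another start. In Table 1 (C1), all PCR-positive cases after the second "shot will be counted and included to estimate vaccine efficacy (primary outcome"). In Table 2 (C2), the wording is nearly the same and again refers to the second dose: those cases after that "shot will be counted and included for the estimation of vaccine efficacy (primary outcome"). Yet the C2 regimen is "SOBERANA-02 vaccine on days 0 and 28 as well as a third dose with SOBERANA-plus on day 56".

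On the analysis population, section 6.2.1 says only that "we will apply by “Intention to treat (ITT)” analysis", which does not fix when counting starts. Section 6.3 reports efficacy as one minus the hazard ratio. All of these are current text, not the amendment record, and nothing states which start takes precedence.

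**The concern.** A primary endpoint needs one start date per cohort. Here the definition gives one date, and a note that explicitly names the primary outcome gives another.

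In C2 the difference is one of substance. The note would bring in 28 days in which participants have had only two doses, plus the 14 days straight after the third. The resulting hazard ratio would mix two-dose and three-dose protection and would no longer estimate the effect of the completed regimen, for which section 6.1 hypothesizes 70%.

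The rules also differ in who can supply an event. Under section 2.4, a PCR-confirmed diagnosis after the last injection bars a further dose. A C2 participant infected between doses 2 and 3 is therefore a primary case under the note, but never reaches 14 days after a third dose.

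**Working it through.** **Planning inputs.** Sections 6.1 and 6.1's Stata commands give a placebo rate of λ₁ = 0.0055 per month, hazard ratios of 0.5 (C1) and 0.3 (C2), a 4:1 ratio, two-sided 0.05 and power 0.90. With loss rate η = −ln(1 − loss)/f over follow-up f, event probability P(λ) = λ/(λ+η) × [1 − exp(−(λ+η)f)], and λ̄ = 0.2λ₁ + 0.8λ₂:

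N = [1.960√V₀ + 1.282√V₁]² / (λ₁ − λ₂)², where V₀ = λ̄²/P(λ̄) × (1/0.2 + 1/0.8) and V₁ = λ₁²/(0.2 P(λ₁)) + λ₂²/(0.8 P(λ₂)).

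- C1: P(λ₁) = 0.01038, P(λ₂) = 0.00521, N = 17,971, against the stated 18,000.
- C2: 5,370 with the inputs as commanded. Without loss it is 4,814, and 4,814/0.8 ≈ 6,018, against the stated 6,000, which is on the safe side of the command.

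The sample size is not at issue here. This step only confirms the planning values reused below.

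**Start of counting (nominal days).**

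| Cohort | Section 4.1 and outcome table | Note 3 | Days added (w) |
|---|---|---|---|
| C1 | 28 + 14 = 42 | 28 | 14 |
| C2 | 56 + 14 = 70 | 28 | 42 (28 before dose 3, 14 after) |

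**Time from dose 2 to the end of efficacy follow-up (T), with a month of 30.4375 days.**

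- C1, three months after dose 2 (section 6.2.5): T = 91.3; w/T = 14/91.3 = 15%.
- C2, four months after dose 3 (section 6.2.5): T = 28 + 121.75 = 149.75; w/T = 42/149.75 = 28%.
- C2, Month 5 (Table 2): T = 152.2 − 28 = 124.2; w/T = 42/124.2 = 34%.

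**Efficacy under the note.** Assume a constant placebo hazard, rare events and no attrition. Let e be the efficacy in the added days and v the later efficacy (0.50 in C1, 0.70 in C2). The estimate is close to the person-time average:

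VE = [w × e + (T − w) × v] / T

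The documents do not give e, so it is varied from zero up to v.

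| e | C1 | C2, to 4 months after dose 3 | C2, to Month 5 |
|---|---|---|---|
| 0 | 42% | 50% | 46% |
| 25% | 46% | 57% | 55% |
| 50% | 50% | 64% | 63% |
| 70% | not applicable | 70% | 70% |

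For example, C2 at e = 0.50 to four months after dose 3 is (42 × 0.50 + 107.75 × 0.70)/149.75 = 96.4/149.75 = 0.644. To Month 5 it is (21 + 82.2 × 0.70)/124.2 = 0.632. Months of 30 days give nearly the same: (21 + 77)/152 = 0.645 and (21 + 56)/122 = 0.631.

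**Expected C2 cases, to four months after dose 3.**

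- Section 4.1 rule: placebo 1,200 × (0.0055/30.4375) × 107.75 = 23.4; vaccine 4,800 × (0.0055/30.4375) × 107.75 × 0.3 = 28.0.
- Note 3 rule: placebo 1,200 × (0.0055/30.4375) × 149.75 = 32.5; vaccine 39.0 if e = 70%, 46.3 if e = 50%, 64.5 if e = 0.

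**The case against.** The strongest reply is that this is an editorial slip and not a rival endpoint. Section 4.1 and the Primary Outcome table are where the endpoint is defined, they agree, and the table is explicit for each cohort. Note 3 is about swabbing logistics. In Table 2 its last sentence looks carried over from the two-dose table; note 2 there has a similar remnant, labelling days 28 and 56 together as the second dose. In C1 the sentence could be a loose reference to the 14-day rule. This is a plausible account of how the conflict arose, but it does not remove it. Both notes name the primary outcome, no precedence is stated, and the C2 sentence points to the wrong dose for that regimen.

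Three stronger readings are tempting but not supported:

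- **That the notes drop the symptom requirement.** They speak of PCR-positive cases, but they belong to the row on monitoring symptomatic COVID-19 and describe swabs from symptomatic volunteers. No screening of asymptomatic participants is described, so the positives meant are those from symptom-triggered testing.
- **That the start date will be chosen after the data are seen.** The statistical analysis plan is not shown and may fix the start. The protocol alone shows only that its text is inconsistent.
- **That efficacy will be off by a known amount.** The shift depends on early efficacy, which the protocol does not state, and it vanishes if early protection already equals later protection.

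**Conclusion.** The contradiction stands, mainly for C2: the last sentence of note 3 conflicts with section 4.1 and the Primary Outcome table on when primary cases begin to count. It adds 42 days in C2 (28% or 34% of the time from dose 2, depending on which stated end of follow-up applies) and 14 days in C1 (15%).

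At the protocol's own 50% two-dose assumption for the added days, C2 efficacy would be estimated at about 63-64% in place of 70%, and C1 would not move. With no early protection the figures would be 46-50% in C2 and 42% in C1. These values are illustrative. They rest on constant hazard, no attrition and an assumed early efficacy. Whenever early efficacy is below later efficacy, the note's rule lowers the estimate, so the shift runs against the vaccine and does not flatter it.

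**What to change.** Amend the last sentence of note 3 in Tables 1 and 2 so that it agrees with section 4.1, the case definition in section 4.1.1 and the Primary Outcome table. Cases counted for the primary outcome would then be symptomatic, PCR-confirmed cases occurring from day 14 after the second dose in C1 and from day 14 after the third dose in C2, with one start date per cohort throughout.

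Cases after dose 2 but before that window may be reported separately as supportive information; resolving the contradiction does not require it.

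The cost is two corrected sentences in an amendment, with no new data and no change to the sample size. The correction fixes the start date only. How participants who never receive their last dose enter the intention-to-treat analysis is a separate matter that the statistical analysis plan may settle.

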#### **4.1.1 Case Definition**

o **Symptomatic COVID-19 infection** is defined as those presenting with two or more of the following symptoms lasting for over 24 hours confirmed with a positive RT-PCR testing: Fever (temperature  $\geq 38^{\circ}\text{C}$ ), chills, new cough, sore throat, nasal congestion, fatigue, muscle or body pain, headache, nausea or vomiting, diarrhea, loss of smell or taste, or at least one respiratory sign or symptom (i.e., cough, shortness of breath, or clinical or radiographic evidence of pneumonia).

o **Severe COVID-19 infection** will be considered as O2 saturation level  $\leq 90\%$ , evidence of lower respiratory disease (e.g., shortness of breath, chest pain or chest tightness) with or without fever  $\geq 38^{\circ}\text{C}$  during clinical assessment or imaging, tachypnea (i.e., respiration rate  $>30$  breaths/min), increased P(A-a) O2 gradient, lung infiltration  $>50\%$  in CT-scans, PaO2/FiO2  $<300$  mmHg, or acute worsening of respiratory symptoms especially dyspnea, respiratory failure, septic shock, and/or multiple organ dysfunction, hospitalization or death due to COVID-19.

o **COVID-19-related Death** will be considered based on the WHO definition: deaths not attributable to another cause (e.g., trauma). There should not be a recovery interval between COVID-19 infection and death.

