## Note

Up to 30% of volunteers with the following conditions can enter the study:

- Obesity (BMI >30 kg/m^2)
- Controlled hypertension (both self-declared and on-site systolic blood pressure <140 mmHg and diastolic pressure < 90 mmHg, the volunteer will be included in the study despite using antihypertensive drugs)
- Chronic renal disease (based on the lab test result in the past six months): GFR: 30-60 CC/min; GFR < 60 will not be included in the study.
- Chronic liver disease that is < 5 folds to the normal range (based on the lab test results in the past six months): AST < 100 U/L, ALT < 150 U/L
- Type 2 diabetes mellitus (based on the lab test result in the past six months): HbA1C < 7.5
- Chronic obstructive pulmonary disease (COPD)
- Controlled asthma (no asthmatic attack in the past three months)
- A history of any malignancy or cancer
- Ischemic heart disease

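### The respiratory limb of the primary case definition drops the new-onset condition that the first limb sets for cough, so a PCR-positive participant with only a long-standing respiratory symptom counts as symptomatic

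*Protocol*

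**What the plan says.** Protocol section 4.1.1 defines symptomatic COVID-19, the primary outcome, by two alternatives.

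- **First limb:** "two or more of the following symptoms lasting for over 24 hours confirmed with a positive RT-PCR testing". The list includes "chills, new cough, sore throat, nasal congestion", so cough must be new and needs a second symptom.
- **Respiratory limb:** "or at least one respiratory sign or symptom (i.e., cough, shortness of breath, or clinical or radiographic evidence of pneumonia". One sign is enough, and neither cough nor shortness of breath has to be new or worse.

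The notes to Table 1 repeat both limbs as the instruction for seeking a PCR test: "in case of presenting with two or more of the following symptoms lasting for over 24 hours confirmed in positive PCR testing", then "or at least one respiratory sign or symptom (i.e., cough", again without an onset condition. They add low oxygen saturation to the respiratory limb, which section 4.1.1 does not. Note 3 to Table 2 (C2) has no symptom list.

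The Note after section 2.3 admits people with "Chronic obstructive pulmonary disease (COPD") and "Controlled asthma (no asthmatic attack in the past three months"), under the rule "Up to 30% of volunteers with the following conditions can enter the study".

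**The concern.** The two limbs treat the same symptom differently. Since they are joined by *or*, the looser one governs: any cough meets the respiratory limb, so the demand in the first limb for a new cough with a second symptom never decides a case. Shortness of breath has no onset condition at all.

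This matters because the trial enrols people in whom a standing cough or breathlessness is foreseeable. If such a participant is tested and is PCR-positive, the written rule classes the infection as symptomatic even when nothing has changed from entry. The endpoint then means something slightly different for participants with chronic respiratory disease, who are part of the underlying-disease subgroup planned in section 6.2.4.

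**Working it through.** The protocol states no figure on this point, so the check is a comparison of its sections.

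**1. Which participants each limb captures**

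| Presentation, with positive RT-PCR | First limb | Respiratory limb | Counted? |
|---|---|---|---|
| New cough plus a second listed symptom, over 24 hours | met | met | yes |
| New cough only | not met | met | yes |
| Long-standing cough only | not met | met | yes |
| Long-standing shortness of breath only | not met | met | yes |
| Sore throat only | not met | not met | no |

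The first row shows the redundancy: whenever cough contributes to the first limb, the respiratory limb is already met. Rows three and four are the unintended cases. As punctuated, the 24-hour duration also attaches only to the first limb.

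**2. Whether another section restores an onset condition**

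- The Primary Outcome table requires viral RNA in samples from suspected cases and adds nothing on onset.
- The notes to Tables 1 and 2 state that every PCR-positive case after the second shot counts towards the primary outcome. Read literally, this bypasses the symptom definition. It also bypasses the counting window, which in the outcome table opens 14 days after the second dose in C1 and after the third dose in C2.
- The severe-case definition in section 4.1.1 does use a worsening condition for respiratory symptoms, which suggests that its absence from the primary respiratory limb is an oversight.

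None of these repairs the wording.

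**3. Direction of the effect**

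This is an illustration on assumed inputs, not an estimate. Let the extra cases with only standing symptoms have a hazard equal to a fraction *f* of the true placebo hazard, the same in both arms, so that the vaccine has no effect on them. Then

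apparent VE = 1 − (HR + f) / (1 + f)

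with HR = 0.5 (C1) and 0.3 (C2) from section 6.1.

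| f (assumed) | C1 | C2 |
|---|---|---|
| 0 | 50% | 70% |
| 0.01 | 1 − 0.51/1.01 = 49.5% | 1 − 0.31/1.01 = 69.3% |
| 0.05 | 1 − 0.55/1.05 = 47.6% | 1 − 0.35/1.05 = 66.7% |
| 0.10 | 1 − 0.60/1.10 = 45.5% | 1 − 0.40/1.10 = 63.6% |

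If the vaccine prevented these infections as well as it prevents symptomatic disease, VE would not move. The protocol gives no share of participants with COPD or asthma, no frequency of standing cough, and no rate of PCR positivity without new symptoms, so it cannot say where in this range, or below it, the trial would fall.

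**The case against.** The strongest reply is that the rule is determinate (one respiratory sign suffices) and that the practical consequence is slight. Much of this stands.

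- **A positive RT-PCR is always needed.** A reader might infer that COPD or asthma alone can produce a case. It cannot: the Primary Outcome table requires viral RNA whichever limb is met. The error is one of label, an infection without new symptoms called symptomatic.
- **Testing follows symptoms.** A reader might also infer that for these participants the endpoint becomes any infection and the test trigger is always on. The documents do not support that. Tables 1 and 2 schedule no routine PCR, swabs are taken from symptomatic volunteers who make contact, and both definition and trigger speak of presenting with symptoms. A participant whose cough is unchanged has no stated occasion to be swabbed.
- **Entry criteria limit the numbers.** Medical conditions must be under control, and recent asthma attacks, heavy long-term smoking and acute infection in the previous seven days are exclusions.
- **The error should be balanced.** Under blinding it would dilute efficacy, not inflate it.

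What the reply does not answer is that the protocol sets an onset condition for cough and then cancels it within the same sentence, and that no other section restores it.

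**Conclusion.** The point holds as a minor defect in the primary case definition. The respiratory limb makes the new-cough entry redundant and allows a PCR-positive participant who presents with only a long-standing respiratory symptom to be counted as symptomatic. The number affected is probably small and cannot be estimated from the documents. The likely consequence is slight dilution of VE, mainly in participants with chronic respiratory disease.

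That direction assumes that blinding holds, so that presentation for testing does not depend on arm, and that the vaccine protects less well against these infections than against new symptomatic disease. A specific loss of efficacy in the underlying-disease subgroup should not be quoted: that subgroup also includes conditions such as obesity, hypertension and diabetes, and the share of cases affected is unknown.

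**What to change.** - **Section 4.1.1:** require the respiratory sign or symptom to be new or clearly worse than at day 0, and state once whether a single new cough is enough or a second symptom is needed. That choice is the sponsor's; the text should carry only one answer.
- **Notes to Table 1 and note 3 to Table 2:** use the same wording for the test trigger in both, and settle whether low oxygen saturation belongs in the definition as well as in the trigger.
- **The counting sentence in both sets of notes:** replace it with cases that meet the section 4.1.1 definition within the cohort's stated counting window. Without this change the reworded limb could still be bypassed.

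The day-0 reference can come from visit 1, where section 3.1.3 already screens all consenting participants for chronic conditions and COVID-19-related symptoms. The timetable lists history of underlying conditions but not cough or breathlessness as such, so these must be recorded explicitly from that screen. The other cost is slightly fewer qualifying cases.

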## **6. Statistical Methods**

### **6.1 Sample Size**

Separate power calculations were performed for the two cohorts. To demonstrate a clinically meaningful difference, we assumed 50% efficacy for two-dose regimens (C1) based on WHO criteria and hypothesized 70% efficacy for the three-dose regimen (C2) based on an independent Technical Support Committee (TSC) opinion that considered the immune response results observed in phases I and II trials of the 2 and 3 dose regimens. Other assumptions included an exponential distribution, minimum baseline incidence of disease in two (0.012) and three-month (0.018) follow-ups (incidence rate: 0.0055 per month), maximum dropout proportion of 10% and 20%, and a vaccine-to-placebo ratio of 4:1. Type I (a two-sided hypothesis) and type II errors of 0.05 and 0.1 were considered for sample size calculation in each cohort. The total sample size was calculated to be about 18,000 participants in C1 (14,400 in the vaccine and 3,600 in the placebo group) and 6,000 participants in C2 (4,800 in the vaccine and 1,200 in the placebo group) using Stata software.

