#### ***Software command for sample size calculation***

Software: Stata (v.14.2)

Cohort 1

power exponential 0.0055, hratio(0.5) power(0.9) nratio(4) fperiod(2) lossprob(0.1) losstime(2)

Cohort 2

power exponential 0.0055, hratio(0.3) power(0.9) nratio(4) fperiod(3) lossprob(0.2) losstime(3)

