## Secondary outcomes

Outcome	Definition	Measurement method	Timing of measurement
Severe COVID-19 infection	Includes severe, critical or hospitalized COVID-19 cases	Included those COVID-19 patients with O 2 saturation level $\leq 90\%$ , evidence of lower respiratory disease (e.g., shortness of breath, chest pain or chest tightness) with or without fever $\geq 38^{\circ}\text{C}$ during clinical assessment or imaging, tachypnea (i.e., respiration rate $>30$ breaths/min), increased P(A-a) O 2 gradient, lung infiltration $>50\%$ in CT-scans, PaO 2 /FiO 2 $<300$ mmHg, or acute worsening of respiratory symptoms especially dyspnea, respiratory failure, septic shock, and/or multiple organ dysfunction, hospitalization or death due to COVID-19.	
C1: From day 14th after the 2nd dose until the end of efficacy study time
 
C2: From day 14th after the 3rd dose until the end of efficacy study time

COVID-19-related death	Based on the WHO definition: The death of a COVID-19 case is not attributable to another cause (e.g., trauma). There should not be a recovery interval between COVID-19 infection and death	Based on the diagnosis of PI and Co-PIs in the cities and approval of DSMB	
Humoral immunity	At least a 4-fold rise in Anti-S1 IgG titer in serum sample compared to the baseline	ELISA	28 days month after the last vaccine shot compared to the serum titer of Day 0
Virus neutralization	Detection of antibodies which can inhibit virus replication (an antibody, which can neutralize virus infectivity)	VNT (Virus Neutralization Test)	On days 0 and 28 days after the second dose, serum samples will be taken from a subset of antibody-positive volunteers and the neutralizing antibody titer will be determined

Cell-mediated immunity (CMI)	Measuring Interferon Gamma secreted from PBMC (peripheral blood cells mononuclear cell)	Interferon Gamma Release Assay (IGRA)	In the cities of Babol and Sari, CMI will be performed
Safety	Frequency of local and systemic adverse events disaggregated by intensity (degree) and seriousness (type)	Case investigation form, Diary form, telephonic follow-up	From day 0 until 5 months after the last dose

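### The severe COVID-19 definition has two symptom-only routes with no severity threshold, so some non-hospitalised, normoxic primary cases also count as severe

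*Protocol*

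**What the plan says.** Efficacy against severe COVID-19 is the first secondary objective. Section 4.1.1 defines the endpoint by a run of criteria separated by commas. Several are measured: oxygen saturation, respiratory rate, alveolar-arterial gradient, extent of CT infiltration and PaO2/FiO2. Among them stands "evidence of lower respiratory disease (e.g., shortness of breath, chest pain or chest tightness) with or without fever", to be seen at clinical assessment or on imaging. The list closes with "or acute worsening of respiratory symptoms especially dyspnea, respiratory failure, septic shock, and/or multiple organ dysfunction, hospitalization or death due to COVID-19". It sets no minimum number of criteria and nowhere requires one item to be combined with another.

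The primary (symptomatic) definition in the same section is met by a positive RT-PCR together with two listed symptoms, or with "at least one respiratory sign or symptom (i.e., cough, shortness of breath, or clinical or radiographic evidence of pneumonia".

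In the Secondary outcomes table, the definition column for severe disease reads "Includes severe, critical or hospitalized COVID-19 cases". The measurement column beside it repeats the list from section 4.1.1, including both symptom items.

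**The concern.** Breathlessness appears in both definitions. If it suffices for each, a participant can be a primary case and a severe case on the same finding, and the measured thresholds elsewhere in the severe list do no work for that participant. The severe endpoint then mixes objectively severe disease with milder illness accompanied by chest symptoms. The protocol's answer on severe disease would be an average over the two, in proportions that nobody has fixed. If the vaccine protects better against truly severe disease, the reported figure would understate that protection.

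**Working it through.** **Step 1. How the list combines.** It cannot be conjunctive, since it ends with hospital admission or death as alternatives. With no minimum count stated, each item is sufficient.

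**Step 2. Which items lack a threshold.** Two symptom-based routes do: lower respiratory disease, for which breathlessness, chest pain and chest tightness are given as examples, and acute worsening of respiratory symptoms. The words on clinical assessment or imaging say where the evidence is seen, not how bad it must be.

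**Step 3. Test cases against both definitions.**

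| PCR-positive participant, normal oxygenation, not admitted | Primary case? | Severe case? |
|---|---|---|
| Shortness of breath found at assessment | Yes, single respiratory symptom | Yes, lower respiratory item |
| Chest tightness at assessment plus two listed systemic symptoms | Yes, two symptoms | Yes, lower respiratory item |
| Cough only | Yes, single respiratory symptom | Not on that symptom |
| Upper-respiratory or systemic symptoms only (two or more) | Yes | No |

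The overlap is real but partial. It survives a stricter reading of the primary definition: if the respiratory clause were just one entry in the two-symptom list, breathlessness plus one further listed symptom would still meet both.

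**Step 4. Look for a correcting step.** The outcome table requires investigator diagnosis and DSMB approval for COVID-19 death but states nothing similar for severe disease. The committee in section 4.3.2 classifies serious and medically attended adverse events for causality; grading COVID-19 severity is not among its stated tasks.

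**Step 5. Illustrate the size.** The protocol gives no event rate, VE or sample size for severe disease, so there is no figure of its own to reproduce. Inputs from section 6.1: "we assumed 50% efficacy for two-dose regimens (C1) based on WHO criteria"; "hypothesized 70% efficacy for the three-dose regimen (C2"); and a 4:1 vaccine-to-placebo ratio. Assumed, not in the protocol: VE_sev, the VE against objectively severe disease; s, the share of placebo severe cases that qualify by symptoms alone; and VE against symptom-only cases equal to the cohort's symptomatic VE (VE_sym). For uncommon events:

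VE_observed = (1 − s) × VE_sev + s × VE_sym

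C1, VE_sev 90%, VE_sym 50%:
- s = 0.25: 0.75 × 0.90 + 0.25 × 0.50 = 0.80
- s = 0.50: 0.50 × 0.90 + 0.50 × 0.50 = 0.70
- s = 0.75: 0.25 × 0.90 + 0.75 × 0.50 = 0.60

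C2, VE_sev 90%, VE_sym 70%:
- s = 0.25: 0.75 × 0.90 + 0.25 × 0.70 = 0.85
- s = 0.50: 0.50 × 0.90 + 0.50 × 0.70 = 0.80
- s = 0.75: 0.25 × 0.90 + 0.75 × 0.70 = 0.75

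With VE_sev 80%, C1 gives 72.5%, 65% and 57.5%, and C2 gives 77.5%, 75% and 72.5%. With VE_sev equal to VE_sym, the result is 50% in C1 and 70% in C2 at every s: no shift.

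**Step 6. Share of events over both arms.** The share s describes placebo only. For C1 with s = 0.75 and VE_sev 90%, in relative units at 4:1:
- objectively severe: 0.25 + 4 × 0.25 × 0.10 = 0.35
- symptom-only: 0.75 + 4 × 0.75 × 0.50 = 2.25
- symptom-only share: 2.25 / 2.60 = about 87%

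**The case against.** **The item requires evidence at assessment or imaging.** Positive participants who do not need admission are followed daily by telephone (footnotes to Tables 1 and 2), so breathlessness first mentioned on a call does not clearly qualify. This stands as a limit on how many cases are affected. It adds no threshold for those who are assessed.

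**The outcome table does not contradict section 4.1.1.** Its measurement column can be read as spelling out its definition column, and the protocol has no other definition of severe. That is fair. The problem is less a clash between columns than a list broad enough to admit people whom the word severe would not ordinarily cover.

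**The endpoint is secondary and unpowered.** Section 6.1 sizes the trial on symptomatic disease only. This is correct, and it limits the weight of the point.

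**Stronger readings go too far.** A reader might infer that mild primary cases in general become severe, or that the endpoint no longer measures severe disease at all. Neither follows: cough-only, upper-respiratory and systemic cases stay out, and every objective criterion stays in. A reader might also infer that severe VE is diluted as a matter of fact, to about 60%. That figure is the C1 result at the largest share tried with VE_sev 90%, and any dilution requires VE to differ by severity, on which the protocol is silent. Nor does a 75% symptom-only share describe all severe events; it is a placebo-arm share.

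**Conclusion.** The point holds in limited form. As written, two symptom-based routes without a severity threshold let a breathless, normoxic, non-hospitalised PCR-positive participant count as severe, so the endpoint does not isolate severe disease. That conclusion rests on the text alone.

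The effect on VE is conditional. If protection is greater against objectively severe disease, reported severe VE moves toward symptomatic VE: by 10 to 30 percentage points in C1 and 5 to 15 in C2 across the assumed shares, with an assumed VE of 90% against severe disease. If protection is equal, VE does not move and only the label is wrong. The protocol supplies neither that VE nor the symptom-only share, so no single size can be claimed. The primary endpoint and sample size are untouched. The definition is worth correcting because it is a stated rule for the first secondary efficacy objective and would misclassify cases if followed exactly.

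**What to change.** In section 4.1.1 and the Secondary outcomes table, in identical words:

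- Remove both symptom-only items as stand-alone routes.
- Define severe disease as PCR-confirmed COVID-19 plus at least one objective criterion already in the list: saturation of 90% or less, respiratory rate above 30, raised alveolar-arterial gradient, CT infiltration above 50%, PaO2/FiO2 below 300 mmHg, respiratory failure, septic shock, multiple organ dysfunction, hospitalisation, or death from COVID-19. The PCR requirement is mainly clarification, since the table already restricts the outcome to COVID-19 patients.
- Report participants who qualify only through lower-respiratory symptoms as a separate category or in a sensitivity analysis, so the broader definition remains visible.

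The change is one of wording, but it has a price: fewer severe events and a wider confidence interval. It also depends on saturation and respiratory rate being recorded for cases managed outside hospital. The footnotes to Tables 1 and 2 describe swabs, possible home assessment and daily telephone contact, but do not schedule those measurements. Where they are not taken, an objectively severe outpatient could be missed.
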